7.5 Justification of sample size

A total of 160 participants in two groups of equal size (80 per group) will be included to compare the efficacy of cysteamine DR vs. placebo with the primary outcome measure of histological improvement in NAS (as defined in section 7.2). A sample size of 160 patients with 1:1 randomization would provide 90% power to the study hypothesis to detect a significant difference between the two groups with a two-sided type I error rate of 0.05. This sample size takes into account that 10% of participants will not have 52 week biopsies and will be considered not improved based upon intention to treat analysis. The sample size estimation is based upon the assumption that the minimum clinically important difference, defined as a 33% lower relative rate of no histological improvement in the cysteamine DR group vs. the placebo group, will be expected with the assumed response rates in the placebo group of 75% (based on TONIC data and 2 to 1 split for patients not taking vs. taking vitamin E at the start of the trial) vs. expected percent with no histological improvement in NAS in the cysteamine DR group to be 50%. These sample size estimations are conservative and would have a minimal likelihood of a type 2 error.

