• The primary analysis is an intention-to-treat analysis in which the proportions of subjects in the active treatment group (cysteamine bitartrate DR orally twice daily) with histological improvement in NAFLD (primary outcome, defined above) is compared with the proportion of subjects in the placebo group in whom there is improvement. The comparison is made using a stratified (by clinical site) Mantel-Haenszel chi-square test; a P-value of 0.05 will be considered statistically significant. Subjects who do not undergo an end-of-treatment biopsy will be counted as not improved.

Sample size and assumptions:

- Total of **160** participants in 2 groups of equal size (**80** per group)
- Primary comparison: cysteamine bitartrate DR vs. placebo
- Primary outcome measure: Histological improvement in NAFLD
- Error protection
- Type I = 0.05
 - Type II = 0.10 (90% power)
- Uncorrected chi-square test using Dupont and Plummer, Power and Sample size software (1998)

Design synopsis

- Missing data: 10% will not have 52 week biopsy and will be considered not improved
- Minimum clinically important difference = 33% relative reduction in percent without clinically important improvement in NAFLD in the active treatment group compared to placebo group.
- Allocation ratio of active treatment to placebo groups = 1:1
- Assumed response rates: Expected percent with no clinically important improvement in NAFLD in the placebo group: 75% (based on TONIC data and assumed background use of medications that may influence histology = 33%)
- Expected percent with lack of clinically important improvement in NAFLD in the cysteamine DR group: 50%

Safety Monitoring

• NIDDK-appointed DSMB will monitor the data for safety and efficacy for outcomes such as hepatotoxicity, pregnancy, and any other outcomes or events identified as safety related.

1. Objectives

We hypothesize that administration of cysteamine bitartrate DR for 52 weeks in children with nonalcoholic fatty liver disease (NAFLD) will result in improvement in liver disease severity as measured by changes in the NAS.

The principal objective of this randomized, multicenter, double-masked placebo-controlled trial is to evaluate whether 52 weeks of treatment with cysteamine DR in children improves NAFLD as measured by changes in histology, compared to treatment with placebo.

Secondary objectives include:

- To assess the safety and tolerability of cysteamine DR in children with NAFLD when given for 52 weeks.

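### The stated 90% power with 10% missing biopsies holds only if 75% and 50% are rates among all randomized children; if they are rates among biopsied children, 160 patients give about 86%

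*Protocol*

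**What the plan says.** Section 7.5 of the protocol sets the size, "A total of 160 participants in two groups of equal size (80 per group"), and says that it "would provide 90% power to the study hypothesis" at a "two-sided type I error rate of 0.05". It then states: "This sample size takes into account that 10% of participants will not have 52 week biopsies and will be considered not improved". The assumed rates are 75% not improved on placebo and 50% on cysteamine DR, and the section closes: "These sample size estimations are conservative and would have a minimal likelihood of a type 2 error".

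The Design Synopsis, under sample size and assumptions, repeats these inputs and names an uncorrected chi-square test with 1:1 allocation. It has separate entries for the error rate, "Type II = 0.10 (90% power"), for missing biopsies, "Missing data: 10% will not have 52 week biopsy and will be considered not improved", and for the placebo rate, "Expected percent with no clinically important improvement in NAFLD in the placebo group: 75"%. The effect of interest is a 33% relative reduction in the percentage not improved.

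The placebo rate is attributed to TONIC data together with background medication use (Synopsis) or a 2 to 1 split by vitamin E use (Section 7.5). Neither place says whether missing biopsies are part of the 75%. The Synopsis (statistical analysis) and Section 7.4 both count children without the 52-week biopsy as not improved in the primary analysis.

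**The concern.** Counting children without a biopsy as failures in both groups pulls the two rates together, so an allowance for it should show either in a larger number or in diluted rates. Neither is shown. The planned 80 per group is close to what 75% versus 50% needs when every child is biopsied.

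This is the protocol's only power statement for its primary test, and it bears on how a null result is read. A reader told that 10% missing has been absorbed, with little chance of a type II error, would put more weight on a negative trial than the design may support.

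**Working it through.** **Inputs** (Section 7.5 and Synopsis): 80 per group; two-sided alpha 0.05; uncorrected chi-square; 75% versus 50% not improved; 10% of each group without a 52-week biopsy, counted as not improved.

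**1. The plan's own figure, rates as stated.** The mean rate is 0.625.
- n per group = [1.96·√(2·0.625·0.375) + 1.2816·√(0.75·0.25 + 0.50·0.50)]² / 0.25² = (1.342 + 0.848)² / 0.0625 = 76.7, so 77 per group, 154 in all.
- Power at 80 per group = Φ[(0.25·√80 − 1.342) / 0.661] = Φ(1.35) = 91.2%. Exact enumeration gives 91.1%.

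The stated 90% therefore reproduces with the rates undiluted. The plan has 160 − 154 = 6 more children than this needs (3.9%). Simple inflation for 10% loss would be 154/0.9, or 172.

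**2. If 75% and 50% are rates among biopsied children.** Apply the missing-biopsy rule.
- Placebo: 0.10 + 0.90·0.75 = 0.775.
- Active: 0.10 + 0.90·0.50 = 0.550.
- The difference falls from 25 to 22.5 points; the mean rate is 0.6625.
- Power at 80 per group = Φ[(0.225·√80 − 1.96·√(2·0.6625·0.3375)) / √(0.775·0.225 + 0.55·0.45)] = Φ[(2.012 − 1.311) / 0.650] = Φ(1.08) = 86.0%. Exact enumeration gives 86.4%.
- n for 90% power = (1.311 + 1.2816·0.650)² / 0.225² = 90.7, so 91 per group, 182 in all.

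Power at 80 per group by the fraction missing:

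| Missing | Power |
|---|---|
| 0% | 91.2% |
| 2% | 90.3% |
| 5% | 88.8% |
| 10% | 86.0% |
| 15% | 82.9% |

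The six extra children cover about 2% missing, not 10%.

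**3. If 75% and 50% are rates among all randomized children, failures for missing biopsy included.** Power is the 91.2% of step 1. Backing out the rates among biopsied children:
- Placebo: (0.75 − 0.10)/0.90 = 72.2%.
- Active: (0.50 − 0.10)/0.90 = 44.4%.
- Relative reduction: 1 − 44.4/72.2 = 38%, against 33% on the all-randomized scale.

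**4. The closing sentence of Section 7.5.** The type II error is 100 − 91.2 = 8.8% on the favourable reading and 100 − 86.0 = 14.0% on the other.

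**The case against.** The strongest reply is that the primary analysis is intention-to-treat with missing counted as not improved, so a group's percentage not improved is naturally a percentage of everyone randomized. On that reading 160 gives at least 90% power, 75% to 50% is a 33% relative reduction, and the 10% is inside both rates. This stands as a permissible reading. The TONIC source behind the 75% is not in the document, so whether that rate already counted missing biopsies as failures cannot be settled here.

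A reader might therefore go too far in three ways:
- *Concluding outright that power is 86% and the 90% is wrong.* That follows only if the rates describe biopsied children, which the text suggests but does not state.
- *Concluding that one stated figure must be wrong whichever reading is taken.* The Synopsis defines the 33% as a comparison of group percentages and does not restrict it to biopsied children. The 38% is a different quantity, which the protocol never gives, so it contradicts nothing.
- *Concluding that 80 is simply 77 rounded up.* The protocol does not say how 160 was reached.

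It is also fair to say that 15% missing exceeds the planned maximum of 10%, and that 86% is still a usual level of power.

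The reply does not remove the ambiguity. The 10% is listed apart from the rates, the basis given for the 75% names no missing-biopsy component, and the 50% is that 75% less one third. All three fit rates among biopsied children better. Nor does the reply support the word conservative: a type II error of 8.8% is close to the nominal 10% even on the favourable reading.

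**Conclusion.** The point holds in conditional form. The claim of 90% power with 10% missing absorbed is true on one unstated reading of 75% and 50% and false on the other.

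- Rates among biopsied children, which the text favours: about 86% power, a type II error of 14% instead of 10%, and 182 children for 90%.
- Rates among all randomized children: about 91% power, but the effect required among biopsied children is 72.2% versus 44.4%, a 38% relative reduction.

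Both results assume exactly 10% missing in each group, equal allocation and the uncorrected chi-square used for sizing. The sentence calling the estimate conservative is unsupported on either reading.

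**What to change.** In Section 7.5 and the Synopsis, state whether 75% and 50% describe biopsied children or all randomized children, and give the matching figure:
- biopsied children: about 86% power with 160 patients when 10% per group lack a biopsy and count as not improved (77.5% versus 55.0%); or
- all randomized children: about 91% power, with a detectable effect among biopsied children of about 72% versus 44%.

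Delete the sentence in Section 7.5 that calls the estimates conservative. These are text changes only: no added enrolment and no change to the analysis. The cost is that the stated power may become less favourable.

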7.6 Interim monitoring

An independent Data and Safety Monitoring Board (DSMB), appointed by the NIDDK, will
P:\Shared\Doc\NASH\CyNCh\Protocol
September 06, 2013
Confidential,
not for distribution
Statistical

review the protocol for the CyNCh trial and monitor the safety data as the trial progresses to ensure patient safety and to review efficacy. The DSMB is a multidisciplinary group with a written charge provided by the NIDDK. The DSMB reports to the NIDDK, which will communicate DSMB recommendations to the investigators, as appropriate. The DSMB will hold a meeting to approve the protocol. After the trial commences, the DSMB will meet twice a year to review data and other issues. The DSMB may request more frequent meetings if necessary to fulfill its charge. It may also request additional safety reports on a more frequent basis. For example, all serious adverse events are reported to the DSMB for their consideration and recommendations as they occur.

Interim data on safety measures requested by the DSMB are reviewed at each of the scheduled semi-annual full meetings. Two additional written safety reports will be reviewed by the DSMB between scheduled full meetings. Serious adverse events will be reviewed by the DSMB as they occur with the option of a teleconference discussion if any DSMB member so requests.

The DSMB will review quarterly reports by masked treatment groups of incident hepatotoxicities, as well as counts of patients who required more frequent liver function testing due to rises in ALT levels of more than 2 times baseline ALT or beyond 400 U/L. The DSMB will also examine the trends in ALT or AST levels for each patient who experiences a rise in ALT.

The DSMB also reviews the overall progress of the trial in terms of recruitment and data quality and makes a formal recommendation to the NIDDK at the end of each scheduled meeting as to whether the trial should continue unmodified, continue with protocol modifications, or be stopped.

8. Human subject issues

8.1 Overview

The study protocol, questionnaires, and consent forms will be submitted to each participating center's IRB. Sites which recruit patients will submit their recruitment materials to their IRB prior to use. A site may not initiate any patient contact about the CyNCh trial until the site has IRB approval for the trial. All study personnel must complete training in the Protection of Human Subjects per NIH guidelines. The proposed study anticipates recruiting a significant proportion of racial/ethnic minorities (African-Americans, Asian-Americans and Hispanics) as well as non-Hispanic white subjects.

8.2 Institutional Review Board (IRB) approvals

A site may not initiate patient screening and randomization activities in the CyNCh trial until the site has IRB approval for the trial and the IND is in effect. Consent forms must have IRB approval. Sites must provide the DCC with a copy of the initial IRB approval notice and subsequent renewals as well as copies of the IRB approved consent statements.

8.3 Informed consent

Template parent consent and pediatric assent documents will be prepared for the trial for screening to determine eligibility with an affirmation of consent for randomization in the trial. Individual sites may add material but may not delete material thought to be necessary for informed consent. Clinics may reformat and reword information to conform to their local requirements. The patient's guardian must sign the consent and the patient must sign the assent to be eligible for the trial. The consent documents will describe the purpose of the trial, the procedures to be followed, and the risks and benefits of participation. Copies of the signed consent/assent forms will be given to the patient and patient's guardian, and this fact will be documented in the patient's record.

8.4 Subject confidentiality

All laboratory specimens, study forms, reports, and other records that are part of the study data collection materials will be identified by coded number to maintain patient confidentiality. All records will be kept in locked file cabinets. All electronic records of study data will be identified by coded number. Clinical information will not be released without written permission of the patient, except as necessary for monitoring by the IRB. Consent procedures and forms, and the communication, transmission and storage of patient data will comply with individual site IRB and NIH requirements for compliance with The Health Insurance Portability and Accountability Act (HIPAA).

10.2 Data Collection schedule

	G		Follow-up visits Weeks from randomizati					
Assessment/Procedure	Screening visits	RZ		f12	f24	f36	iizatio f52	n f76
Consent and HIPAA authorization	X	112	101	112		100	102	1/0
Baseline medical history	X	•	•	•	•	•	•	•
Follow-up medical history			X	X	X	X	X	X
Review for adverse effects		•	X	X	X	X	X	X
Review for concomitant medications	X	X	X	X	X	X	X	X
Alcohol questionnaire AUDIT (A) if interim (I)	А		Ι	Ι	Ι	Ι	Ι	Ι
Detailed (D) or focused (F) physical exam	D	F	F	F	D	F	D	D
Liver biopsy*	X*						Х	
MRI for hepatic fat (optional)	Х						Х	
Nutritional assessment	Х						Х	
Pediatric quality of life	Х						Х	Х
Liver symptoms questionnaire	Х			Х	Х	Х	Х	Х
Standard of care materials provided		Х						
Eligibility confirmation		Х						
Study drug dispensing		Х	Х	Х	Х	Х		
Review of study drug adherence			Х	Х	Х	Х	Х	
Labs:								
Complete blood count	Х		Х.	Х	Х	.X	Х	Х
Comprehensive metabolic panel with uric acid	Х				Х	•	Х	Х
Hepatic panel with GGT, PT, INR	Х		Х	Х	Х	Х	Х	Х
Fasting lipid profile	Х				Х	•	Х	Х
Fasting serum glucose, HbA1c, and insulin	Х				Х	•	Х	Х
Etiologic tests	Х					•	•	
Pregnancy test	Х	Х	Х	Х	Х	Х	Х	
Banking:								
Fasting serum and plasma	Х			Х	Х	Х	Х	Х
DNA	Х							
Liver tissue	Х	•	•	•			Х	
Closeout form	•	•	•	•	•	•	•	Х

Complete blood count: Hemoglobin, hematocrit, mean corpuscular volume (MCV), white blood cell count (WBC), white blood cell differential, platelet count

Comprehensive metabolic panel: calcium, carbon dioxide, chloride, glucose, potassium, sodium, creatinine, blood urea nitrogen (BUN), uric acid

Hepatic panel: Total bilirubin, direct bilirubin, aspartate aminotransferase (AST), alanine aminotransferase (ALT), alkaline phosphatase, gamma glutamyltransferase (GGT), albumin, total protein, prothrombin time (PT), international normalized ratio (INR)

Lipid profile: triglycerides, total cholesterol, LDL and HDL

Etiologic tests: Hepatitis B surface antigen, hepatitis C antibody, alpha-1-antitrypsin level, ceruloplasmin. Autoantibodies: (ANA, AMA ASMA), serum iron, ferritin and total iron binding capacity (TIBC)

*The liver biopsy during screening is for the patient's clinical evaluation of NAFLD

		Study visit (wk)						
Procedure	Screening	f04	f12	f24	f36	f52	f76	Total
Fasting glucose, HbA1c and insulin	5			5		5	5	20
Fasting lipid profile	5	•	•	5	•	5	5	20
Complete blood count	5	5	5	5	5	5	5	35
Comprehensive metabolic panel	5	•		5		5	5	20
Hepatic panel with GGT, PT, INR	5	5	5	5	5	5	5	35
Etiologic tests	20				•	•	•	20
Plasma	10		10	10	10	10	10	60
Serum	20		20	20	20	20	20	120
DNA	20					•	•	20
Total	95	10	40	55	40	55	55	350

10.3 Blood collection schedule (amounts in mL)

Complete blood count: Hemoglobin, hematocrit, mean corpuscular volume (MCV), white blood cell count (WBC), white blood cell differential, platelet count

Comprehensive metabolic panel: calcium, carbon dioxide, chloride, glucose, potassium, sodium, creatinine, blood urea nitrogen (BUN), uric acid

Hepatic panel: Total bilirubin, direct bilirubin, aspartate aminotransferase (AST), alanine aminotransferase (ALT), alkaline phosphatase, gamma glutamyltransferase (GGT), albumin, total protein, prothrombin time (PT), international normalized ratio (INR)

Lipid profile: triglycerides, total cholesterol, LDL and HDL

Etiologic tests: Hepatitis B surface antigen (HBsAg), hepatitis C antibody (anti-HCV), alpha-1antitrypsin level, ceruloplasmin. Autoantibodies: (ANA, AMA, ASMA), serum iron, ferritin, and total iron binding capacity (TIBC) Glossary

10.4

A1AT	alpha-1-antitrypsin
ALT	alanine aminotransferase
AMA	antimitochondrial antibody
ANA	anti-nuclear antibody
anti-HCV	hepatitis C antibody
ASMA	anti-smooth muscle antibody
AST	aspartate aminotransferase
AUDIT	Alcohol Use Disorders Identification Test
BMI	body mass index (kg/m ²)
BUN	blood urea nitrogen
CC	Clinical Center
CRN	Clinical Research Network
DCC	Data Coordinating Center
DDC	Drug Distribution Center
DSMB	Data and Safety Monitoring Board
EMT	epithelial-mesenchymal transition
GCRC	General Clinical Research Center
GGT	gamma glutamyltransferase
HbA1c	hemoglobin A1c
HBc	hepatitis B core antigen
HBsAg	hepatitis B surface antigen
HCC	Hepatocellular carcinoma
HCV	hepatitis C virus
HIPAA	Health Insurance Portability and Accountability Act
INR	international normalized ratio
IRB	institutional review board
MCV	mean corpuscular volume
MRI	magnetic resonance imaging
MRS	magnetic resonance spectroscopy
NIH	National Institutes of Health
NAFL	nonalcoholic fatty liver
NAFLD	nonalcoholic fatty liver disease
NAS	nonalcoholic fatty liver disease activity score
NASH	nonalcoholic steatohepatitis
NSAIDs	nonsteroidal anti- inflammatory drugs
PPARγ	peroxisome proliferator-activated receptor-gamma
PT	prothrombin time
ROS	reactive oxidative species
SAE	serious adverse event
SOC	standard of care
TIBC	total iron binding capacity
WBC	white blood cell count

10.5 Document History

Cysteamine Bitartrate Delayed-Release for the Treatment of Nonalcoholic Fatty Liver Disease (NAFLD) in Children (CyNCh) Trial Protocol (08 March 2012)

Cysteamine Bitartrate Delayed-Release for the Treatment of Nonalcoholic Fatty Liver Disease (NAFLD) in Children (CyNCh) Trial Protocol (13 April 2012)

Numerous editorial and wording changes were made to the following sections

- IND #114,924 was added to the cover page and section 6.9
- Corrected spelling of maldondialdehyde to malondialdehyde throughout

§ Design Synopsis

- Removed "serum" from pregnancy test in inclusion and exclusion criteria
- Added seizure disorder as an exclusion criteria
- Added gastrointestinal ulcers/bleeding as an exclusion criteria
- Added Clinically significant depression (patients hospitalized for suicidal ideations or suicide attempts within the past 12 months) as an exclusion criteria

§ 4.3 Exclusion criteria

- Added seizure disorder
- Added gastrointestinal ulcers/bleeding
- Added Clinically significant depression (patients hospitalized for suicidal ideations or suicide attempts within the past 12 months)
- Removed "serum" from pregnancy test

§ 5.4 Follow-up visits

- Added complete blood count to follow-up visits at Week 4, Week 12, and Week 36
- Removed phosphate from metabolic panel

§ 10.2 Data Collection schedule

- Added complete blood count to follow-up visits at Week 4, Week 12, and Week 36
- Removed phosphate from metabolic panel

§ 10.3 Blood collection schedule

- Added complete blood count to follow-up visits at Week 4, Week 12, and Week 36
- Adjustments made to estimated blood draw amounts
- Removed phosphate from metabolic panel

§ 10.5 Document History

• Added document history

Cysteamine Bitartrate Delayed-Release for the Treatment of Nonalcoholic Fatty Liver Disease (NAFLD) in Children (CyNCh) Trial Protocol (06 September 2013)

§ Design Synopsis

- Changed Recruitment phase from 9 to 19 months
- Changed Follow-up phase: from 27 to 37 months

- § 3.5 Primary Endpoint changed to Primary outcome measure
 - Clarified primary outcome measure to: "Centrally scored and masked assessment of histologic improvement in NAFLD between the baseline liver biopsy and follow-up biopsy after 52 weeks of treatment, where improvement is defined as: (1) decrease in NAS of 2 or more and (2) no worsening of fibrosis."
- § 3.6 Secondary Endpoints changed to Secondary outcome measures
- § 4.1 Recruitment
 - Changed recruitment period to 19 months
- § 5.2 Screening and baseline data collection: Screening visit
 - Removed albumin, total protein from metabolic panel and added to hepatic panel
 - Added "Three separate 24 hour food recalls will be obtained during screening."
- § 5.4 Follow-up visits
 - Removed albumin, total protein from metabolic panel and added to hepatic panel at Week 24, Week 52 and Week 72 visits.
 - Added albumin, total protein to hepatic panel at Week 4, Week 12, and Week 36 visits
 - Clarified that three separate NDSR 24 hour food recalls will be obtained at Week 52 visit
- § 5.5 Questionnaires
 - Clarified that three separate NDSR 24 hour food recalls will be obtained during screening and at Week 52 visit

§ 6.2 Safety issues in children with NAFLD taking delayed release cysteamine bitartrate (RP103) capsules

- Added: RP103 was approved by the FDA in April 2013 for the treatment of nephropathic cystinosis (Raptor Therapeutics Inc., PROCYSBI (cysteamine bitartrate delayed release capsules, Investigator's Brochure, April 2013).
- § 7.2 Outcome measures
 - Primary outcome measure revised to: The primary outcome measure, improvement in NAFLD from the start of treatment to the end of treatment at 52 weeks, is defined for each patient as:
 - Improvement in NAS score by 2 or more points, and
 - No worsening of the fibrosis score
 - All secondary outcome measures were expanded to express changes from baseline to end of treatment in the cysteamine group compared to the placebo group
- § 7.3 Statistical analysis
 - Primary hypothesis changed to Primary outcome measure
 - Secondary outcomes statistical analyses were added to detail the planned statistical approach for each secondary outcome measure to determine changes from baseline to end of treatment in the cysteamine group compared to the placebo group

- § 10.1 Participating centers
 - Changed investigator at Texas Children's Hospital, Houston, TX
 - Changed NIDDK Data Repository contractor
- § 10.2 Data Collection Schedule
 - Removed total protein from metabolic panel and added to hepatic panel
 - Corrected spelling of "transferease" to transferase
- § 10.3 Blood Collection Schedule
 - Removed total protein from metabolic panel and added to hepatic panel
 - Corrected spelling of "transferease" to transferase
